Additional Endpoints	
I.) Providers:
 
 a. System Usability Scale (SUS) retained in its standardized format b. Obi Medical Device Needs Assessment (MDNA) Form, and the overall service delivery process per SOP220. c. Optional - Semi-Structured Interview 
II.) Caregivers:
 
 a. System Usability Scale (SUS) retained in its standardized format b. Modified Matching Person and Technology (MPT) assessment. The standardization of this tool is no longer retained given the changes made, but will still provide valuable data regarding the caregivers'

	
impressions of Obi Gen 3 following the one week trial period.
 
c. Optional - Semi-Structured Interview
 
III.) Patients
 
a. Modified Matching Person and Technology (MPT) assessment. The standardization of this tool is no longer retained given the changes made, but will still provide valuable data regarding the patients' impressions of Obi Gen3 following the one week trial period.
 
b. Descriptive data regarding the patient-participants will be gathered from their completed MDNA Form.
 
c. Optional - Semi-Structured Interview

Inclusion Criteria	
 - Providers with relevant expertise to recommend and evaluate patients' ability to use Obi - Caregivers directly assisting users with Obi - Adults or children (≥ 5 years) needing assistive feeding technology to self feed
Exclusion Criteria	
 - Inability to provide informed consent/assent - Cognitive impairments that may prevent the ability to understand or respond to the survey questions - Non-English speakers (English-only materials) - Residents of California who are new Obi users

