This clinical investigation is a non-randomized, non-comparative usability study designed to evaluate whether the Obi Gen 3 Medical Robotic Feeding Device conforms to its intended use and meets documented user needs. The purpose of the study is not to assess therapeutic effectiveness or to compare outcomes across intervention groups but to validate device usability and stakeholder satisfaction across real-world settings.

Given the nature and objectives of the study, randomization, blinding, and allocation concealment are not applicable. However, several measures will be taken to minimize or avoid bias and manage potential confounding factors:

1. Standardized Protocols and Training

All participants (providers, caregivers, and patients) will engage with the device under a standardized study protocol, including consistent onboarding materials, instructional documents, and usage expectations (e.g., a minimum of five meals during the trial period). These materials were developed based on prior formative feedback and are provided in uniform formats to reduce variability in participant experience.

2. Structured Data Collection Tools

Usability feedback will be collected using validated instruments (e.g., System Usability Scale, Matching Person & Technology framework) and semi-structured interview guides. These tools ensure consistency in gathering information, reduce interviewer bias and facilitate comparisons across stakeholder groups.

3. Triangulation of Stakeholder Perspectives

The study design allows for triangulation of findings by including data from three distinct stakeholder groups (providers, caregivers, and patients). This multi-perspective approach reduces the risk of single-source bias and provides a broader understanding of device usability in real-world contexts.

4. Post-Use Feedback After Trial Exposure

Participants provide their usability ratings and feedback only after completing the one-week trial. This approach helps minimize expectation bias and ensures responses reflect the user experience with the device.

5. Blinding of Data Analysts (if applicable)

The Principal Investigator will conduct the data analysis but will not be involved directly in participant recruitment or data collection, reducing the potential for confirmation bias during the interpretation of results.

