- **Providers** - Licensed healthcare professionals with direct experience in recommending, assessing, or implementing assistive technology, rehabilitation interventions, or feeding-related supports. This may include, but is not limited to, occupational therapists (OTs), speech-language pathologists (SLPs), assistive technology professionals (ATPs), and other qualified providers actively engaged in supporting individuals with self-feeding challenges.
- **Caregivers** - Individuals who provide regular, hands-on support to a person who may benefit from using the Obi Gen 3 device. This includes family members, personal care aides, educational support staff, or other support personnel who assist with or supervise feeding activities in the home, school, or community setting.
- **Patients:** Adults or children aged 5 years or older who require assistive technology to support independent or supported self-feeding due to upper extremity motor impairments or related

functional limitations. Individuals must have the cognitive and physical ability to participate in the one-week usability trial, either independently or with the assistance of a caregiver.

All participants must be able to understand and comply with study instructions and provide consent or assent (when applicable) either by themselves or through a legally authorized representative.

b) Exclusion Criteria for Subject Selection

Participants will be excluded from the study if they meet any of the following conditions:

- Individuals who cannot provide informed consent or assent, either due to legal status, cognitive limitations, or other conditions that impair decisional capacity.
- Individuals with severe cognitive impairments that would preclude meaningful participation in the study's usability tasks, including the ability to interact with the device or provide relevant feedback.
- Non-English-speaking individuals, as all study materials—including consent documents, surveys, and instructions—are available only in English at this time, and interpreter services are not being utilized in this investigation.
- California residents who are new to using Obi. The state of California requires a one-month trial, so the one-week timeline will not be feasible for California residents.

c) Criteria and procedures for subject withdrawal or lost to follow-up

i) when and how to withdraw a subject from the clinical investigation or stop the use of the investigational device,

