Each subject's participation in the clinical investigation will vary based on their role (provider, caregiver, or patient) and level of engagement. The core duration of participation for all enrolled stakeholders is approximately one week, corresponding to the required trial period of the Obi Gen 3 Medical Robotic Feeding Device in a home, school, or community setting.

- **Patients and Caregivers:** Participants are expected to use the device for at least five meals over a one-week period. During this time, they will use the device in real-life contexts and later complete post-trial surveys and optional follow-up interviews.
- **Providers:** Participating providers are expected to conduct an initial in-office assessment to determine patient suitability for the Obi Gen 3, recommend at least one patient for trial use, and provide feedback based on their clinical observation. Their involvement also includes completing a usability survey post-trial and, if applicable, participating in a brief follow-up interview.

Follow-up through telephone-based semi-structured interviews may be conducted within one month to further clarify or expand responses to open-ended questions. These interviews will be scheduled within one month of the trial's completion.

h) Number of subjects required to be included in the clinical investigation, and where needed, anticipated distribution of enrolment among the participating investigation sites.

A total of 60 participants will be recruited using flyers and word-of-mouth strategies

Stakeholder Group	Target Sample Size
Providers [Occupational Therapists (OTs), Assistive Technology Professionals (ATPs), Speech Language Pathologists (SLPs), and other relevant providers)	20 in various practice settings
Caregivers (family members, aides, support personnel)	20 (5 for adults, 15 for children)
Patients (adults and children using Obi Gen 3)	20 (5 adults, 15 children)

i) Estimated time needed to select this number (i.e. enrolment period).

The estimated time required to enroll the whole sample for this usability study is 4–5 weeks, given the study's targeted outreach strategy, electronic recruitment methods, and existing professional and caregiver networks available to DESIN LLC and the investigative team. Recruitment materials, including flyers and direct outreach, will be distributed electronically and through participating service providers to expedite enrollment.

j) Relationship of investigation population to target population.

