Although this study does not include formal repeated-measures testing or time-stamped use logs, reported experience over multiple uses (i.e., across several meals and settings) will provide insight into how effectively users can learn to operate the device independently. This data will inform training recommendations and design refinements to support intuitive, low-burden use in real-world environments.

g) Pass/fail criteria to be applied to the results of the clinical investigation.

As a design validation study, the primary objective of this clinical investigation is to determine whether the Obi Gen 3 production equivalent device meets its formally documented user needs and intended use across three key stakeholder groups: patients, caregivers, and providers. The pass/fail criteria are based on usability outcomes aligned with ISO 13485 and FDA design validation requirements. The following criteria must be met for the device to be considered as having “passed” the clinical investigation:

Primary Endpoints: Acceptance criteria is based on safety and quality risk (see IFD-DES-054-1, Design Validation Plan, and IFD-DES-054-2, Design Validation Protocol). Note: Design Validation planning involves more than just human subject testing. This CIP covers only the human subject portion.

Intended Use: For all subjects that complete the 1-week trial, the following must be met:

- ICF performance qualifier for Functional Eating must drop at least one severity level (ex. “severe” to “moderate”) for 85% of patients.
- No Serious Adverse Device Effects (SADE), Serious Health Threat, or Unanticipated Serious Adverse Device Effect (USADE).

User Needs: For all subjects that complete the 1-week trial, 50% of respondents must be in favor that the requirement has been fulfilled (see IFD-DES-051-1 Validation Plan)

If the investigation meets or exceeds these thresholds across all stakeholder groups, the design will be deemed to have passed and is considered validated. If one or more criteria are not met, the results will be analyzed to determine if design modifications, additional training resources, or workflow adjustments are necessary prior to commercialization.

h) The provision for an interim analysis, criteria for the termination of the clinical investigation on statistical grounds, where applicable.

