- Meal spillage or choking risk due to poor positioning or inadequate supervision in certain user

These events are considered low risk, especially when users are screened appropriately and receive training. Mitigation strategies include:

- Device orientation and training prior to use
- Provider oversight during setup and monitoring
- Encouragement of caregiver presence during early use

i) Emergency contact details for reporting serious adverse events and serious adverse device effects.

See sponsor contact information, A.1.3.

j) Information regarding the DMC, if established.

Given the minimal risk nature of this study and the non-interventional design, a formal Data Monitoring Committee (DMC) has not been established. All safety oversight will be managed internally by the Principal Investigator in collaboration with the sponsor. Any unexpected safety issues or emerging risks will trigger an ad hoc safety review, and the IRB will be informed accordingly.

A.15. Vulnerable Population (if applicable)

a) Description of the vulnerable population to be included in the clinical investigation.

This clinical investigation includes participation by children aged 5 years and older who require assistive technology for self-feeding. Children are considered a vulnerable population under federal and international research guidelines due to their limited legal capacity to provide informed consent and their potential dependence on caregivers and authority figures. Additionally, the study may include adults with disabilities, another potentially vulnerable group, particularly if cognitive or communication challenges are present.

b) Description of the screening process to identify and protect the vulnerable population.

Pre-screening will be conducted by qualified clinical staff in accordance with SOP220, which includes assessment of developmental, cognitive, and physical ability to participate meaningfully in the usability trial. Only individuals who demonstrate the ability to interact with the Obi Gen 3 device with or without assistance and are capable of participating in basic study activities (e.g., completing feeding tasks, expressing feedback with support) will be included. For all participants, providers will verify that participation is voluntary and appropriate given the individual's medical, cognitive, and psychosocial context. Caregivers and/or legal guardians will be involved in the initial screening and enrollment decision.

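### The protocol admits patients who give feedback with support but does not define that support or record whose answers a patient form holds, so a separate patient verdict on user needs is not secured.

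*Protocol*

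**What the plan says.** **Who may enter.** Three passages set the standard for patient feedback, and they differ.

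- The exclusion list in the synopsis (A.1.5) reads: "Cognitive impairments that may prevent the ability to understand or respond to the survey questions".
- A.6.3 b) excludes only severe cognitive impairment that precludes meaningful participation, "including the ability to interact with the device or provide relevant feedback".
- A.15 b) sets the screening floor: patients are in if they are "capable of participating in basic study activities (e.g., completing feeding tasks, expressing feedback with support) will be included". A.15 a) adds that adults with disabilities may be a vulnerable group, "particularly if cognitive or communication challenges are present".

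**Where help is mentioned.** A.6.3 a) says: "Individuals must have the cognitive and physical ability to participate in the one-week usability trial, either independently or with the assistance of a caregiver". That concerns the week of device use and does not mention the survey.

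**Who answers.** The synopsis has patients completing the patient survey, through a web link sent after the trial. A.1.2 lists separate adult and child patient surveys, whose content is not shown.

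**Numbers.** A.6.3 h) plans patients as "20 (5 adults, 15 children" and caregivers in the same split. A.6.4 a) recruits providers, caregivers and patients together where possible.

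**What depends on separate voices.** A.7 g) requires that "50% of respondents must be in favor that the requirement has been fulfilled", and the design passes if the thresholds are met in all stakeholder groups. A.7 j) analyses the three groups separately to keep roles from confounding one another. A.6.1 b) item 3 relies on three distinct groups: "This multi-perspective approach reduces the risk of single-source bias".

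**The concern.** The patient survey goes by web link to people whose upper-limb impairment is serious enough to need feeding technology. Three quarters of them are children, some perhaps as young as five. Help with many of these forms is to be expected, and the person at hand will often be the caregiver, who may also be enrolled and completing the caregiver form.

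Help with reading or typing does no harm. Help that becomes answering for the patient does: that dyad then contributes one opinion twice, and the patient row of the user-needs result contains a caregiver's view. Agreement between the two forms would look like corroboration when it is duplication. A.6.4 c) item 4 itself names caregivers and providers as the groups most likely to give favourable feedback out of social desirability. Its remedies, anonymised surveys and neutral interviewing, do not address who fills in the patient form.

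This cannot be left to the analysis stage. If the form does not record whose answers it holds, no later method can separate them.

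**Working it through.** **1. The plan's own figures.** Groups: 20 + 20 + 20 = 60 (A.6.3 h). Patients: 5 + 15 = 20; children's share 15/20 = 75%. The human-factors guidance quoted in A.7 e) suggests at least 15 per distinct user population. With 10% drop-out, the upper bound in A.7 e) 6), 15/0.9 = 16.7, so 17 per group are needed and 20 suffice. These figures hold if all 20 patient forms are patients' own.

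**2. How many own voices remain.** Let k be the number of patient forms answered by an enrolled caregiver. The protocol gives no value for k, so this is a range. Own-answer patients = 20 − k; distinct respondents in the study = 60 − k.

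| k | own-answer patients | distinct respondents |
|---|---|---|
| 0 | 20 | 60 |
| 5 | 15 | 55 |
| 10 | 10 | 50 |
| 15 (all children) | 5 | 45 |
| 20 | 0 | 40 |

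The own-answer group falls below 15 once k exceeds 5.

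**3. Leverage on the 50% rule.** With 20 respondents the mark is 0.5 × 20 = 10 in favour. The 15 child forms alone are enough to reach or miss it.

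**4. Illustration on assumed rates.** The documents give no favour rates, so these show mechanism only. Let patients favour a need with probability a and caregivers with probability c, independently, and let k forms carry the caregiver's answer. Then P(patient group passes) = P(X + Y ≥ 10), with X ~ Bin(k, c) and Y ~ Bin(20 − k, a).

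| a, c | k = 0 | k = 10 | k = 15 |
|---|---|---|---|
| 0.40, 0.60 | 0.245 | 0.590 | 0.754 |
| 0.40, 0.70 | 0.245 | 0.761 | 0.923 |
| 0.60, 0.40 (gap reversed) | 0.872 | 0.590 | 0.407 |
| 0.50, 0.50 | 0.588 | 0.588 | 0.588 |

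The effect can help or hurt the device, and with equal rates it vanishes for the patient group taken alone.

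**5. Joint passing with equal rates.** Even at a = c = 0.50, shared answers make the two groups pass together more often. If independent, 0.588² = 0.346. With 15 shared answers it is 0.478, and with all 20 shared it is 0.588. This is the loss of triangulation, and it needs no gap between the groups.

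**6. The three entry standards side by side.** A patient who can give feedback only when someone helps phrase the answer could fail the synopsis exclusion (may be unable to respond to the questions), pass A.6.3 b) (impairment not severe) and pass A.15 b) (feedback with support). The passages do not settle whether that patient is eligible or what the helper may do.

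**The case against.** A reader might infer that the protocol lets caregivers answer for patients, or that A.7 g) counts helper-answered forms as patient responses. The documents do not support either reading. The screening sentence in A.15 b) names no supporter and no survey, and support may mean typing, reading aloud or a communication aid. The synopsis says patients complete their own survey, and its exclusion is aimed at those who could not. The caregiver help in A.6.3 a) concerns the device trial. A.7 g) speaks only of respondents and is silent on helpers. The adult and child surveys are not shown and may already ask who is answering.

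The overlap is also partial. Full triads are encouraged but not required, so some patients may have no enrolled caregiver. Caregivers include aides and school staff, so the survey helper may be someone outside the study. Provider data stay separate in any case. The probabilities rest wholly on assumed rates and reverse if caregivers are less favourable than patients.

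All of this stands, and it limits the point to an undefined term and an unrecorded source of answers. It does not remove the point. The synopsis exclusion concerns cognition, not physical access to a web form. The body of the protocol applies a looser standard than the synopsis. A separate child form does not show who filled it in.

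**Conclusion.** The point holds as a gap in definition and recording. The protocol states three different standards for patient feedback, leaves the permitted support undefined, and in the text shown has no means of telling a patient's own answers from a helper's. Proxy answering is foreseeable but not authorised, and its frequency is unknown.

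For any dyad in which the enrolled caregiver answers for the patient, the separate patient result and the single-source-bias argument fail. For other dyads they are unaffected. Neither the size nor the direction of any effect on the pass/fail outcome can be stated from the documents. What is certain is that children are 75% of the planned patient group and so could decide its result. The change is inexpensive and worth making before data collection; confidence is medium, because the survey instruments are not shown.

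**What to change.** 1. Reconcile the synopsis exclusion, A.6.3 b) and A.15 b) into one standard for a patient's ability to answer the survey.
2. State that help with reading or entering answers is allowed, and that the answers must be the patient's own.
3. Unless the surveys already have it, add one required item to the adult and child patient surveys: answered by me; my own answers, entered by a helper; answered for me by a helper (give role).
4. In A.7 g), report the patient user-needs result twice, for own-answer forms (the first two categories) and for all patient forms, and show helper-answered forms separately.
5. In A.6.1 b) item 3, limit the triangulation claim to own-answer forms.

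Cost: one survey item and some wording. The own-answer group will be smaller and its proportion less precise. It may fall below the 15 cited in A.7 e), to 5 if every child's form were helper-answered; if so, the report should say so. For that reason both results should be shown, rather than helper-answered forms being dropped outright.

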Appendix A: DESIN LLC's Document References

DOC#	TITLE	REV	ECO
SOP220	TRIAL ASSESSMENT PROCEDURE	1.1.0	167-6
SOP210	COMPUTER SECURITY PROCEDURES	1.0.0	157
SOP200	PRIVACY PROCEDURES	1.0.0	157
SOP170	SAFETY RISK MANAGEMENT PROCEDURE	2.0.0	122
SOP120	RETURN AND SERVICE PROCEDURE	3.0.1	138
SOP110	RECORDS	2.2.0	157
SOP080	CAPA PROCEDURES	1.2.0	152
SOP070	NON-CONFORMANCE PROCEDURES	1.2.0	122
SOP020	DOCUMENT CONTROL PROCEDURE	1.2.0	122
SOP010	DESIGN CONTROLS	1.2.0	122
NA	SGS SAFETY CERTIFICATION (SAFETY & EMC)	NA	NA
NA	CONSULTING AGREEMENT, DESIN LLC & ADAPTIVE DRIVING SOLUTIONS	NA	NA
NA	CERTIFICATE OF INSURANCE, DESIN LLC	NA	NA
IFD-DES-080	DESIGN REVIEW, OBI3 VERIFICATION	1.0.0	172-16
IFD-DES-070	FORMATIVE EVALUATION REPORT, OBI3	1.0.0	172-8
IFD-DES-064	FORMATIVE EVALUATION PLAN, OBI3	1.0.0	172-6
IFD-DES-054-1	DESIGN VALIDATION PLAN, OBI3	1.1.0	172-18
IFD-DES-053-2B-R2	DESIGN VERIFICATION RESULTS, OBI3 (TRIAL 2)	1.0.0	172-18
IFD-DES-053-2B-R1	DESIGN VERIFICATION RESULTS, OBI3	1.0.0	172-16
IFD-DES-053-2A-R1	DESIGN VERIFICATION RESULTS, OBI3	1.0.0	172-16
IFD-DES-025	MARKETING REQUIREMENTS	5.6.0	172-18
IFD-DES-022	SAFETY RISK MANAGEMENT REPORT	2.1.0	122
IFD-DES-021	OBI CLINICAL EVALUATION PLAN & REPORT	3.0.0	167-5
IFD-DES-018	PRODUCT HAZARDS ANALYSIS	5.1.0	172-5
IFD-DES-003	OBI SAFETY RISK MANAGEMENT PLAN	3.0.0	172-3
IFD-DES-001	OBI US REGULATORY PLAN	2.1.2	167-1
IFD-801-012	OBI TRAVEL ROUTER	5.4.1	167-4
IFD-700-003	OBI CONTROL BOARD SOFTWARE, RELEASE NOTES	7.1.0	172-17
IFD-600-003	INSTRUCTIONS FOR USE	5.1.0	172-18
IFD-600-002	QUICK START GUIDE	2.0.0	172-14
IFD-400-110	UTENSIL ADAPTER, OBI3	1.0.0	172-10
IFD-400-108	SPORK, OBI3	1.1.1	172-11
IFD-400-102	SMALL SPOON, OBI3	1.1.1	172-11
IFD-400-101	LARGE SPOON, OBI3	1.1.1	172-11
IFD-400-100	CLASSIC SPOON, OBI3	1.1.1	172-11
D-FRM-005	COMPLAINT FORM	2.0.0	138
Cert#6026	ISO13485 CERTIFICATE	NA	NA

